For those patients who do not meet criteria for a Gambling Disorder, we will proceed to have patients complete a self-administered online Timeline Followback to assess the past 21 days of alcohol use. Patients who drink an average of at least 7 drinks per week, will proceed with further screening. This may include a mini-SCID to assess for alcohol use disorder (among patient with an AUDIT-C>4) (strong correlation with AUD)⁵⁹; a PHQ-9 to assess for depressive symptoms; and an assessment for smoking. Patients not otherwise meeting criteria who have not had labs drawn within the prior 60 days, may be asked to have an HIV viral load, HCV (antibody or RNA as indicated) and/or necessary labs to determine whether they have evidence of liver scarring by FIB-4 (AST, ALT, and platelets, FIB>1.45).

Consent for PEth: Potentially eligible patients who are HIV-positive, able to provide informed consent and meet any of the criteria for unhealthy alcohol use, and none of the exclusion criteria will be asked to undergo a PEth analysis.

Consent to enroll: If the PEth is > 20 ng/ml patients will be asked to provide written informed consent for study participation and enroll in the trial.

Randomization: Eligible participants will be randomly assigned to CM plus stepped care or TAU by the Yale Center for Analytic Sciences (YCAS). Participants will be randomized using a stratified randomization procedure with stratification by site and drinking category (at-risk, medical conditions impacted by alcohol, AUD) as they may be associated with outcomes. We have implemented this process in prior studies.^{60,61}

Treatments

Table 2. Comparison of CM plus stepped care and Treatment as usual (TAU)

Step	Treatment Service	CM	TAU
1	Referrals as needed by HIV provider	Y	Y
1	CM counseling	Y	N
1	Reward for PEth < 8 ng/ml	Y	N
1	Reward for addressing medical conditions impacted by alcohol	Y	N
2	Addiction Physician Management	Y	N
2	MET	Y	N

CM plus stepped care arm

Counseling Overview

CM will be provided according to established principles and procedures.²⁵⁻²⁷ These include using: 1) contracts that identify target behaviors (e.g. abstinence), 2) objectively quantified behavioral outcomes (breathalyzer or saliva test and PEth), 3) valued rewards, 4) successive approximations to reward progress toward goals, and 5) withholding rewards when target behaviors are not achieved.^{26,27}

Contingency Management Visits and Procedures

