General considerations: This is a randomized, controlled, parallel group trial to evaluate the effectiveness of CM plus stepped care compared to TAU to reduce unhealthy alcohol use in HIV-infected individuals. Data analysis will be conducted by [name] and YCAS. The 6-month follow-up was chosen as the primary endpoint as we expect the most robust differences at this time and there is uncertainty in the shape of the treatment response over time. Average intervention group differences across all time points and slopes of change will be compared between groups in supportive secondary analysis. A type I error of 5% (two-sided) will be used to test for significance and analyses will be performed using SAS v9.2 (SAS Institute, Cary, NC).

Adequacy of sample size

The primary aim of the study is to determine whether CM plus stepped care will lead to a greater proportion of patients with PEth documented abstinence when compared to TAU. The primary outcome will be proportion of patients with self reported abstinence on Timeline Follow Back at 6 months, with PEth < 8 ng/ml at 6 months as a secondary outcome (Aim 1). Data from the TAU group in the **STEP** Trials, when restricted to those with a PEth > 20 ng/ml at baseline, reveals 11% spontaneous abstinence as assessed using PEth < 8 ng/ml at 6 months. We believe this provides a good estimate of the anticipated abstinence rate with TAU in the proposed trial. To detect a 15% difference (proportion demonstrating abstinence in CM plus stepped care of 26%) with 80% power at a two-sided 0.05 significance level, a sample size of 139 per group is required. Thus, we will enroll and randomize 348 patients to account for 20% dropout. Based on alcohol consumption in the TAU arms of the **STEP** Trials, and a standard deviation of 11.5, we will have 80% power to detect a difference of 3.9 in average drinks per week over the last 30 days, at 6 months. Data from the TAU group in the **STEP** Trials reveals that 29% of patients

experienced a 5-point decrease in the VACS Index at 6 months. With the proposed sample size, we will have 90% power, at a two-sided 0.05 significance level, to detect a 20% difference in this (Aim 2) outcome (proportion of patients who achieve a 5-point decrease in the VACS Index in CM plus stepped care of 49%). In our prior trials, including the **STEP** Trials, we have obtained completed 6-month assessments in 74-95% of enrolled subjects.^{60,61}

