Baseline comparability: Because of the sample size, we expect the randomization process will produce reasonably comparable groups. However, the adequacy of the randomization will be assessed by comparing the distribution of baseline demographic and clinical characteristics among the intervention groups. Comparability for continuous variables will be examined graphically and by summary statistics (means, medians, quartiles, etc.). Categorical variables will be examined using frequency distributions. If we find differences in baseline characteristics, we will conduct a sensitivity analysis employing covariate adjustment.¹¹⁰

Interim monitoring: Interim monitoring will focus on recruitment, adherence to protocol, baseline comparability of treatment groups, completeness of data retrieval, and uptake of the assigned intervention. A set of monitoring tables will be generated by YCAS for this purpose. No interim looks for efficacy are planned.

Analysis for Aim 1: The primary objective of the analysis is to determine if the proportion of individuals with self reported abstinence on the Timeline Follow Back differs between those assigned to CM plus stepped care compared to those receiving TAU. Abstinence will be assessed using PEth at 3, 6, 9 and 12 months after randomization as a secondary outcome.

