A likelihood-based ignorable analysis using a generalized linear mixed model (GLMM) will be used to compare abstinence between groups.^{111,112} The primary advantage of the mixed model when compared to commonly used methods such as complete case analysis and single imputation (e.g. last observation carried forward) is its flexibility in handling missing data. This analysis makes use of all available outcome data at each timepoint and assumes that missing data occurs at random (i.e. not informative).¹¹³ The inclusion of 3, 6, 9 and 12 month outcome data in the model will assist in meeting this assumption. More specifically the mixed models will include fixed effects for intervention (CM plus stepped care vs. TAU), time (3, 6, 9, 12 months), and the interaction of intervention with time. Additional fixed effects will be included for baseline covariates: PEth, stratification group (at-risk drinking, medical condition impacted by alcohol, AUD), number of drinks per week, gender, VACS index and study site. Given the heterogeneity in the patient groups, the interaction between intervention and stratification group will be evaluated and included in the primary analysis at the p<0.10 significance level. Linear contrasts will be used to estimate intervention group differences and 95% confidence intervals at the primary 6-month outcome assessment. Similar contrasts will be performed at the other secondary follow-up times and supportive analyses examining the average and slope of change in abstinence rates across post-randomization time will be performed. Subgroup analyses will be performed to evaluate moderation of the intervention response by stratification group and study site. We will also use linear mixed effect models to compare continuous PEth and alcohol consumption using data from the TLFB.

Analysis for Aim 2: The primary objective of Aim 2 is to determine if HIV biomarkers (VACS index) differ between subjects receiving CM plus stepped care compared to those receiving TAU. The primary response will be defined as a 5-point improvement from baseline on the VACS index. As in Aim 1, a GLMM will be used to compare this response. We will use a repeated measures mixed model analysis with continuous VACS index as the outcome. As in Aim 1, we will perform subgroup analyses to evaluate moderators.

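### A p<0.10 pretest decides whether the primary model contains an intervention-by-stratum term, and the weights for the overall 6-month contrast are then not stated

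*Combined protocol and SAP*

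**What the plan says.** Analysis for Aim 1 sets out a generalized linear mixed model with intervention, time (3, 6, 9 and 12 months) and intervention-by-time. Its baseline covariates include the three-level stratification group: at-risk drinking, medical condition impacted by alcohol, and AUD. The plan then adds a rule: "the interaction between intervention and stratification group will be evaluated and included in the primary analysis at the p<0.10 significance level". The reason offered for this rule is "Given the heterogeneity in the patient groups". The sentence that follows the rule is "Linear contrasts will be used to estimate intervention group differences and 95% confidence intervals at the primary 6-month outcome assessment". Shortly after it comes "Subgroup analyses will be performed to evaluate moderation of the intervention response by stratification group and study site".

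Three other places bear on what the primary contrast should be:

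- The opening of Analysis for Aim 1, which compares the two arms: "The primary objective of the analysis is to determine if the proportion of individuals with self reported abstinence on the Timeline Follow Back differs".
- Adequacy of sample size, which sizes the trial on one comparison: "To detect a 15% difference (proportion demonstrating abstinence in CM plus stepped care of 26%) with 80% power".
- Randomization (Section V, item 3), which gives "stratification by site and drinking category (at-risk, medical conditions impacted by alcohol, AUD) as they may be associated with outcomes".

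Nowhere does the plan give weights for combining the three stratum effects, expected stratum sizes, or a statement on whether the added term is also crossed with time.

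**The concern.** The trigger is prespecified, but the analysis that follows it is not. Without the term, the 6-month intervention contrast is a single number. With it, there are three stratum-specific contrasts, and any overall one depends on whether they are weighted by stratum size, weighted equally, or read off at a reference stratum by software default. An analyst who has seen the stratum results could choose, and either choice can be the favourable one depending on which stratum responds.

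The objective and the sample size both describe one overall comparison, and moderation by stratum already has its own subgroup analysis. The pretest therefore adds no information that the plan would otherwise lack, yet it makes the primary effect conditional on the data. Heterogeneity between strata is the plan's own reason for the rule, and it is also the condition under which the unstated weights matter.

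**Working it through.** **Inputs from the documents.** TAU 11%, intervention 26%, two-sided alpha 0.05, 139 per group, three strata (a 2-df interaction), pretest at 0.10.

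**The plan's own figure.** The usual two-proportion formula, with mean proportion 0.185, is n = [z₀.₉₇₅√(2 × 0.185 × 0.815) + z_power√(0.11 × 0.89 + 0.26 × 0.74)]² / 0.15².

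- 80% power: (1.0763 + 0.4535)² / 0.0225 = 104.0, so 105 per group (117 with continuity correction).
- 90% power: (1.0763 + 0.6905)² / 0.0225 = 138.7, so 139 per group.

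The stated 139 is thus the 90% figure, although the text says 80%. That is a separate matter; 139 is used below only as the stated number. The total is consistent: 278 / 0.8 = 347.5, so 348.

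**Assumptions.** The documents give no stratum shares or stratum effects. Main shares are 20/30/50%. Pattern A has intervention rates of 16/26/36% by stratum and pattern B has 36/26/16%, with TAU at 11% throughout.

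**Contrasts.** With the term in the model, stratum log odds ratios θ₁, θ₂, θ₃ with variances v₁, v₂, v₃ give Δ = Σwₖθₖ and SE = √(Σwₖ²vₖ), where wₖ is either the sample share or 1/3. The two weightings target different effects. In percentage points:

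- Pattern A, sample weights: 0.2 × 5 + 0.3 × 15 + 0.5 × 25 = 18.
- Pattern B, sample weights: 0.2 × 25 + 0.3 × 15 + 0.5 × 5 = 12.
- Equal weights, either pattern: (5 + 15 + 25) / 3 = 15.

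**Single-time-point simulation.** Logistic model, 1:1 within strata, 2-df likelihood-ratio pretest, Wald contrasts, 0.5 added in strata with an empty cell, 100,000 trials per scenario.

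- Null (11, 20 or 30% in both arms; shares equal, 20/30/50% or 10/30/60%): the term enters in 10.5-13.7%. Type I error is 4.5-5.0% without the term, 4.5-5.1% for pretest with sample weights and 4.5-6.0% for pretest with equal weights.
- A normal approximation to the null gives 5.3% (20/30/50%), 6.1% (10/30/60%) and 6.9% (5/25/70%) for equal weights. Reading one stratum's coefficient as the effect gives 5.8-8.3%.
- Common effect, 11% vs 26%: the weightings disagree on significance in 0.0, 1.2 and 3.5% of all trials for the three share sets.
- Half-size patterns (21/26/31% or 31/26/21%): the term enters in 16-17%; disagreement in 1.8-3.0% of all trials.
- Equal-sized strata: disagreement in at most 0.7% of the trials in which the term enters.

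**Four-visit mixed model.** Random-intercept logistic model (SD 2, assumed), 5,000 trials per scenario. Rates are either constant over visits, or the difference at 3, 9 and 12 months is half that at 6 months. The second case follows the plan's own expectation under General considerations: "we expect the most robust differences at this time and there is uncertainty in the shape of the treatment response over time". Null type I error was 4.5-4.8% without the term, 4.5-4.9% with sample weights and 4.6-5.2% with equal weights.

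Results for patterns A and B, as a percentage of all simulated trials:

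| Scenario | Term enters | Power, no term | Power, pretest + sample weights | Power, pretest + equal weights | Weightings disagree |
|---|---|---|---|---|---|
| A, single time point | 29.0 | 97.1 | 95.4 | 87.0 | 8.3 |
| B, single time point | 31.7 | 77.4 | 74.0 | 80.7 | 6.9 |
| A, mixed model, constant | 50.3 | 96.8 | 96.2 | 88.3 | 7.9 |
| B, mixed model, constant | 54.0 | 75.7 | 73.8 | 82.1 | 8.3 |
| A, mixed model, peak at 6 months | 32.2 | 97.0 | 96.8 | 92.9 | 3.9 |
| B, mixed model, peak at 6 months | 35.0 | 75.8 | 75.4 | 80.7 | 5.4 |

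Among single-time-point trials in which the term enters, power is 90.8% (sample) vs 62.0% (equal) in A and 65.4% vs 86.8% in B. The weightings then disagree in 28.8% and 21.7% of those trials. A repeat of the single-time-point runs with 60,000 trials gave disagreement of 8.4% (A) and 6.7% (B) of all trials; the mixed-model runs were not repeated.

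**The case against.** The strongest reply is that the rule is prespecified, has a stated reason, and does little by itself. With sample weights, the pretest procedure and the model without the term reach different conclusions in only 0.2-0.3% of null trials, 0.4-0.5% under a common effect, 0.7-0.8% for the half-size patterns, and 1.9% (A) and 3.7% (B) under strong heterogeneity. The larger losses come from equal weights, so naming the weights would close the open choice. This stands, and it shows that the unstated contrast is the larger part of the defect. It does not remove the other part: the primary model would still be chosen by a test on the outcome.

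Second, the plan does not say outright that the contrast is pooled. Stratum-specific contrasts would need no weights. That reading is possible, but it fits poorly with a single objective, a single sample-size comparison and a separate subgroup analysis. It would also leave the primary test undefined, since nothing says which of three results decides.

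Third, the sizes rest on assumed shares and patterns, and part of the disagreement reflects two different target effects rather than error. Both points are correct. The second is also the reason the target should be fixed in advance.

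**Conclusion.** The concern holds and should be fixed. The primary model depends on a pretest, and once the term enters, the plan does not define the overall 6-month contrast.

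The size is modest and conditional. It is negligible with equal-sized strata, and small with a common effect or mild heterogeneity. With unequal strata that truly differ, the choice of weights changes significance in roughly 4-8% of all trials and moves power in either direction: sample weights do better in pattern A and equal weights in pattern B. This is not mainly a type I error problem.

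The simulations omit baseline PEth, drinks per week, gender, VACS index, site and missing data, so they show direction and approximate size only. That the weights are missing from the plan does not depend on any of these assumptions.

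**What to change.** Delete the p<0.10 inclusion rule from the primary analysis. State that the primary 6-month contrast comes from the model with intervention, time, intervention-by-time and the listed covariates including stratification group, without the intervention-by-stratum term, whatever the interaction p-value. Report the interaction test and stratum-specific estimates with confidence intervals in the planned subgroup analysis. Date the change before anyone sees outcome data by arm.

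The cost is one sentence; no patients or data are lost, and the interaction is still tested and reported. In patterns A and B this model has 1.7 and 3.4 points more power than the pretest with sample weights at a single time point, and 0.2-1.9 points more in the mixed model. The drawback is that the primary estimate is a common effect and does not show stratum differences. Nor is it the most powerful choice everywhere. In pattern B the pretest with equal weights does better (80.7% vs 77.4% at a single time point, 82.1% vs 75.7% in the mixed model with constant rates), but in pattern A it loses 10.1 and 8.5 points respectively.

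Second best is always to include the term and name one sample-weighted 6-month contrast. This fixes the target but can cost power: in pattern B, 70.2% vs 77.4% (single time point), 72.9% vs 75.7% (mixed model, constant) and 74.5% vs 75.8% (peaking).

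The minimum is to keep the rule and name the weights. That removes the open choice but leaves the primary model dependent on a pretest.

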Hypothesis 2: CM plus stepped care will lead to a greater proportion of patients who experience at least a 5-point decrease in the VACS Index.

Aim 3 (Exploratory): Among patients with medical conditions adversely impacted by alcohol, to compare the impact of CM plus stepped care vs. TAU on measures including detectable HIV viral load, urine cotinine and anabasine (for smoking cessation), FIB-4, detectable HCV, depressive symptoms and use of psychoactive medications that interact with alcohol.

2. **Background:** Describe the background information that led to the plan for this project. Provide references to support the expectation of obtaining useful scientific data.

Patients with unhealthy alcohol use identified by screening are not motivated to stop drinking

Many HIV-infected patients are unaware of the harms associated with their alcohol use.¹ They have stable drinking patterns² putting them at ongoing risk for adverse effects from alcohol yet are not motivated to change their drinking. This is especially true among individuals coming for routine medical visits to address other priorities¹ who are identified with unhealthy alcohol use via screening. HIV-infected patients indicate that alcohol consumption serves a number of functions (e.g. coping and facilitating social interactions).³

Alcohol use in HIV-infected patients can adversely impact HIV and other medical conditions

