Analysis for Exploratory Aims: For aim 3, we will evaluate the impact of the intervention in those with medical conditions on condition-specific outcomes such as HIV viral load, eCO or urine cotinine (for smoking cessation), FIB-4, detectable HCV virus, depressive symptoms and use of psychoactive medications that interact with alcohol. These analyses will focus on estimation rather than hypothesis testing and will be performed only in those identified with the specific medical condition at baseline. GLMMs will be used to describe these outcomes by treatment group and time. Treatment differences for continuous outcomes, odds ratios for dichotomous outcomes and rate ratios for count outcomes along with 95% CIs will be estimated.

Plan for Missing Data: Several strategies will be imposed to accommodate the likelihood of missing data. Prevention is the most effective manner to control bias and loss of power from missing data.¹¹⁴ In our prior alcohol trials we have obtained 6 month assessments in 95% and 88% of subjects.^{60,61} We will follow the intent to treat principle, requiring follow-up of all subjects randomized regardless of the treatment received.¹¹⁵ Telephone and text visit reminders will be sent to participants prior specified collection times. Timely data entry combined with weekly missing data reports will trigger protocols for tracking and obtaining missing data items. Despite these efforts it is reasonable to assume missing data will occur. Our primary analysis is valid under the assumption that missing data is missing at random (MAR).¹¹¹ We will evaluate the plausibility of this assumption by determining the extent of missing data and use logistic regression to identify factors associated with dropout. While we do not expect differential dropout rates between groups or high loss to follow-up, we will perform sensitivity analysis using pattern-mixture and selection models under missing not at random (MNAR) assumptions to examine the robustness of conclusions of the primary analysis to missing data.

Timeline and Milestones

SECTION VI: RESEARCH INVOLVING DRUGS, BIOLOGICS, RADIOTRACERS, PLACEBOS AND DEVICES

If this section (or one of its parts, A or B) is not applicable, state N/A and delete the rest of the section.

A. DRUGS, BIOLOGICS and RADIOTRACERS

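### The models for the continuous Aim 3 outcomes (PHQ-9, FIB-4, and viral load or exhaled CO if analysed as levels) do not name the outcome's own baseline value, so intervals will be somewhat wider than they need be

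*Combined protocol and SAP*

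**What the plan says.** Section V, item 9 (Statistical Considerations), Analysis for Exploratory Aims, gives the Aim 3 model in one sentence: "GLMMs will be used to describe these outcomes by treatment group and time". The analyses "will be performed only in those identified with the specific medical condition at baseline". Their purpose is also stated: "These analyses will focus on estimation rather than hypothesis testing". The output is to be: "Treatment differences for continuous outcomes, odds ratios for dichotomous outcomes and rate ratios for count outcomes along with 95% CIs will be estimated".

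The Aim 3 statement in Section V, item 1 mixes continuous and presence/absence outcomes: "measures including detectable HIV viral load, urine cotinine and anabasine (for smoking cessation), FIB-4, detectable HCV, depressive symptoms", together with use of psychoactive drugs that interact with alcohol.

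Three other places bear on the point:

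- **Analysis for Aim 1** does list covariates: "Additional fixed effects will be included for baseline covariates: PEth, stratification group", then "number of drinks per week, gender, VACS index and study site". It sets time at 3, 6, 9 and 12 months.
- **Baseline comparability** says: "If we find differences in baseline characteristics, we will conduct a sensitivity analysis employing covariate adjustment".
- **The assessment schedule (Table 3)** has the PHQ-9, viral load, FIB-4 components and the exhaled CO or cotinine test at baseline and at every follow-up.

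**The concern.** In the Aim 1 model the plan adjusts for baseline PEth and baseline drinks per week, the starting values of the drinking outcomes. For Aim 3 it names no equivalent. PHQ-9 score and FIB-4 are continuous, are measured at baseline, and still vary among patients above the entry cut-offs (PHQ-9 above 9, FIB-4 above 1.45). Part of the spread at follow-up is therefore predictable from the starting value, and a model without that value leaves it in the error term.

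Because Aim 3 is about estimation, the interval is the product. A wider interval in a subset that may hold only a fraction of the 348 patients makes an already tentative estimate less informative. Randomization is stratified by site and drinking category, not by individual condition, so nothing in the design balances baseline PHQ-9 or FIB-4 within its own subset.

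**Working it through.** **Does another part of the plan supply the baseline value?** The Aim 1 covariates are PEth, stratification group, drinks per week, gender, VACS Index and site. None is the PHQ-9, FIB-4, viral load or CO. Table 3 lists viral load and the FIB-4 components in the VACS Index row, so baseline VACS would be a partial proxy for those two and no proxy for the PHQ-9. The Baseline comparability clause applies only if differences are seen, and only as a sensitivity analysis.

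**Is there a figure in the plan to reproduce?** No. Aim 3 has no sample size, SD, correlation or subset size. The correlations, degree of truncation and subset sizes below are assumptions.

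**Step 1. Gain from adjustment.** For a linear model and the contrast at one visit, adjusted variance / unadjusted variance = 1 − c², where c is the baseline-to-follow-up correlation within the subset. The interval narrows by 1 − √(1 − c²). The equivalent multiple of the sample size is 1/(1 − c²).

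**Step 2. Allow for the entry cut-offs.** Selecting patients above a cut-off shrinks the baseline variance and so lowers the correlation. Under bivariate normality, with full-range correlation r and baseline variance reduced to a fraction v, c² = r²v / (r²v + 1 − r²). Keeping the top 50%, 30% or 20% gives v = 0.363, 0.264 or 0.219.

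Example, r = 0.7 and top 50%: r²v = 0.49 × 0.363 = 0.178; c² = 0.178 / (0.178 + 0.51) = 0.259; c = 0.51; narrowing = 1 − √0.741 = 13.9%.

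| Full-range r | Subset kept | c | CI narrower by | Equivalent sample size |
|---|---|---|---|---|
| 0.5 | top 50% | 0.33 | 5.6% | 1.12× |
| 0.5 | top 30% | 0.29 | 4.1% | 1.09× |
| 0.5 | top 20% | 0.26 | 3.5% | 1.07× |
| 0.7 | top 50% | 0.51 | 13.9% | 1.35× |
| 0.7 | top 30% | 0.45 | 10.7% | 1.25× |
| 0.7 | top 20% | 0.42 | 9.1% | 1.21× |
| 0.85 | top 50% | 0.70 | 28.3% | 1.95× |
| 0.85 | top 20% | 0.60 | 20.2% | 1.57× |

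Without the allowance for truncation, r = 0.7 would give 29%, which overstates the likely gain here.

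**Step 3. In units of the outcome SD.** For an assumed subset of 80 (40 per arm), the unadjusted half-width is 1.96 × √(2/40) = 0.44 SD. With r from 0.5 to 0.7 it becomes 0.42 to 0.38 SD. For an assumed 200, the half-width is 0.28 SD unadjusted and 0.27 to 0.24 SD adjusted.

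**Step 4. Chance imbalance.** With N patients in two equal arms, the SD of the baseline mean difference is √(4/N), which is 0.22 baseline SD at N = 80. An imbalance reaches the follow-up difference multiplied by c: 0.22 × 0.26 = 0.06 up to 0.22 × 0.51 = 0.11 outcome SD. The unadjusted interval already contains this variation. It is the same loss as in Step 2, not an additional one.

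**Step 5. Presence/absence outcomes.** Everyone in the subset has the condition at baseline. Detectable HCV, detectable viral load, smoking status and interacting-medication use are then constant in their own subsets. A constant covariate explains nothing, so the gain is zero.

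**The case against.** **The plan is silent; it does not exclude baseline.** This stands. A reader might infer that Aim 3 uses treatment and time and nothing else, but the sentence says how outcomes will be described and does not claim to list every term. The 3, 6, 9 and 12 month definition of time belongs to Aim 1, so baseline could be intended as a repeated response. That alone would not settle the matter. If the arm means at baseline are left free, then with complete data the follow-up contrast is still the unadjusted one. The gain comes only if baseline means are constrained equal or baseline is a covariate, and the plan would have to say which.

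**Most listed outcomes are not continuous.** This also stands. A reader might extend the point to every Aim 3 measure. Step 5 shows why that fails. Nor does the narrowing carry over to odds ratios: adjusting a logistic model for a prognostic covariate does not shrink the standard error of the log odds ratio, and it changes the odds ratio being estimated.

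**Bias from small, unbalanced subsets.** A reader might infer bias. The documents do not support that. Randomization keeps the unadjusted difference unbiased, and no prevalence or subset size is given, so even smallness is an inference.

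**Imbalance is already handled.** Only in part. The Baseline comparability clause acts after the data are seen, is not specific to Aim 3, and leaves the unadjusted estimate as the main one.

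**The aim is exploratory.** True. No primary or secondary conclusion depends on it, which sets the weight of the point.

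**Conclusion.** The point holds for the continuous Aim 3 outcomes only: PHQ-9 score and FIB-4, and HIV RNA or exhaled CO if analysed as levels. For these the plan names no adjustment for the outcome's own baseline value, and no other section supplies it. The cost is precision. The confidence interval is wider than necessary by an amount that adjustment would cut by about 4% to 14%, equivalent to 1.07 to 1.35 times the patients. This assumes full-range correlations of 0.5 to 0.7, truncation to the top 20% to 50%, normality and a linear model. At a correlation of 0.85 the cut would be 20% to 28%, but nothing in the documents supports a particular value. Severity is minor: this is a nearly free improvement to an exploratory aim.

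**What to change.** In Section V, item 9, Analysis for Exploratory Aims, add a sentence to this effect: each continuous Aim 3 outcome will be modelled with its own baseline value, either as a fixed effect or as a baseline response with means constrained equal across arms, and the resulting adjusted difference will be the reported estimate. Name the scales: PHQ-9 score, log FIB-4, and log10 HIV RNA or CO level where these are analysed as levels. State also what time includes in these models. Presence/absence outcomes that are constant at baseline in their subset need no such term.

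The cost is one sentence. Table 3 already schedules the baseline measurements. Fixing the adjustment in advance also removes any choice about it after the data are seen.
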